9.0 STUDY PLAN

9.1 Study Procedures

The following sections describe the study procedures and data to be collected. For each procedure, subjects are to be assessed by the same investigator or site personnel whenever possible. The Schedule of Study Procedures is located in [Appendix A](#).

The timing of planned procedures for assessment of safety procedures (eg, vital signs, ECG, safety laboratory tests) currently outlined in the protocol may be modified during the study based on newly available safety, tolerability, PK, or PD data (eg, to obtain data closer to the time of peak plasma concentrations). These changes may increase the number of study procedures for a given subject during his/her participation in the entire study.

If additional days of dosing or confinement are required based on emerging data, the following at a minimum would be collected daily; AE assessment, concomitant medication assessment, vital signs, Bristol stool scale, and ECG.

If additional safety laboratory or PK samples are obtained, the total blood volume should not exceed a total blood volume of 550 mL.

9.1.1 Informed Consent Procedure

The requirements of the informed consent are described in Section [15.2](#).

Informed consent must be obtained prior to the subject entering into the study and before any protocol-directed procedures are performed, including requesting that a subject fast for laboratory evaluations.

A unique subject identification number (subject number) will be assigned to each subject at the time that informed consent is obtained; this subject number will be used throughout the study.

9.1.1.1 Pharmacogenomics Informed Consent Procedure

Pharmacogenomics (PGx) informed consent is a component of the overall study informed consent. The requirements are described in Section [15.2](#).

PGx sample collection is mandatory.

9.1.2 Demographics, Medical History, and Medication History Procedure

Demographic information to be obtained will include date of birth, sex, Hispanic ethnicity, race as described by the subject, height, weight, caffeine consumption, alcohol use, reproductive status (including last menstrual period), and smoking status of the subject at Screening.

Medical history to be obtained will include determining whether the subject has any significant conditions or diseases relevant to the disease under study that stopped at or prior to signing of informed consent. Ongoing conditions are considered concurrent medical conditions (see Section [9.1.8](#)).

For subjects in Cohort 16, the following medical history will be collected: diagnosis, date of diagnosis, MMSE score, date of onset of donepezil treatment, and dose and timing of administration of donepezil (evening [bedtime] required).

Medication history information to be obtained includes any medication relevant to eligibility criteria stopped at or within 28 days prior to signing of informed consent.

9.1.3 Physical Examination Procedure

A physical examination will consist of the following body systems: (1) eyes (see more details in Section 9.1.3.1); (2) ears, nose, throat; (3) cardiovascular system; (4) respiratory system; (5) GI system; (6) dermatologic system; (7) extremities; (8) musculoskeletal system; (9) nervous system; (10) lymph nodes; and (11) other.

Any abnormal finding on a pretreatment physical examination assessment must be assessed as not clinically significant or clinically significant by the investigator and recorded in the source document and eCRF. All clinically significant findings/changes will be recorded as a PTE or concurrent medical condition in the source document and on the appropriate eCRF described in Section 10.0 or Section 9.1.8.

On subsequent examinations, any abnormal change from the pretreatment physical examination assessment occurring immediately prior to the start of the investigational drug must be assessed as not clinically significant or clinically significant by the investigator and recorded in the source document and eCRF. Any clinically significant change or new diagnosis as a result of a clinically significant change, as determined by the investigator, will be recorded as an AE in source documentation and on the PTE/AE eCRF described in Section 10.0.

9.1.3.1 Funduscopy (Cohorts With CSF Sampling Only)

A Baseline ophthalmological assessment of the retina (funduscopy) will be performed at Screening for subjects enrolled in cohorts for CSF sampling. Funduscopy will be performed by a trained person (optometrist, ophthalmologist, or neurologist) after dilatation of the pupil in both eyes by administration of tropicamide 0.5% eye drop. After pupil dilatation, subjects will be advised to wear sunglasses for the next 4 to 6 hours and avoid operating a car.

9.1.4 Weight, Height, and BMI

A subject should have weight and height measured while wearing indoor clothing and with shoes off. The Takeda standard for collecting height is centimeters without decimal places and for weight it is kilograms with 1 decimal place.

BMI should be derived as follows: $BMI = \text{weight (kg)} / [\text{height (m)}]^2$.

Note that although height is reported in centimeters, the formula uses meters for height; meters can be determined from centimeters by dividing by 100. Thus, for example, if height=176 cm (1.76 meters) and weight=79.2 kg, then $BMI = 79.2 / 1.76^2 = 25.56818 \text{ kg/m}^2$.

The values should be reported to 1 decimal place by rounding. Thus, in the above example BMI would be reported as 25.6 kg/m². However, if the BMI is used to satisfy the entry criteria, then this determination must be made after rounding.

9.1.5 MMSE

The MMSE is an 11-question tool that tests 5 areas of cognitive function: orientation, registration, attention and calculation, recall, and language. The maximum score is 30, with lower scores indicating more cognitive impairment [22]. The MMSE will be administered at Screening to subjects in Cohort 16 only by trained site personnel.

9.1.6 Vital Sign Procedure

In subjects who are not undergoing CSF collection (Cohorts 2, 4 to 8, and 10 to 22), vital signs will include body temperature (oral), respiratory rate, and orthostatic blood pressure and pulse (bpm).

In subjects who have completed enrollment for Cohort 1 at the time of this amendment and in subjects who are undergoing CSF collection (Cohorts 3 and 9), vital signs include body temperature (oral), respiratory rate, supine blood pressure (resting more than 5 minutes), and pulse (bpm).

Vital signs should be collected daily, predose and upon morning rising on days during confinement. In addition, vital signs should be collected in Cohorts 3 and 9 at approximately 5 hour postdose on Day 1 and Day 8 (Cohort 9 only). Vital signs may be repeated. All measurements will be recorded on the source documents and in the eCRF.

When vital signs are scheduled at the same time as blood draws, the blood draw will take priority, and vital signs will be obtained within 0.5 hour before the scheduled blood draw.

For BA/FE Cohort 17, for the fed regimen, if vital signs coincide with a meal, vital signs will take precedence followed by the meal.

For Cohorts 2, 4 to 8, and 10 to 22, orthostatic blood pressure and pulse will be measured at predose and at 2, 4, 6, 8, and 12 hours postdose in the first 24 hours after the initial dose of TAK-071 (Day 1) and then afterwards on days while subjects are in the phase 1 unit. Orthostatic blood pressure will be measured as follows [23]:

1. Have the patient lie down for 5 minutes.
2. Measure blood pressure and pulse rate.
3. Have the patient stand.
4. Repeat blood pressure and pulse rate measurements after standing 1 and 3 minutes.

A drop in bp of ≥ 20 mm Hg, or in diastolic bp of ≥ 10 mm Hg, or experiencing lightheadedness or dizziness is considered abnormal [23].

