6.2 Justification for Study Design, Dose, and Endpoints

6.2.1 Study Design

This phase 1 study is randomized, double blind, and placebo controlled to avoid subjective bias in the assessment of safety and tolerability and pharmacological effects of the study drug. Placebo will be administered as a control in order to establish the frequency or magnitude of changes in clinical endpoints that may occur in the absence of active treatment.

The study will be initiated as an SRD (Cohorts 1 to 6, 18, and 19) so that each enrolled subject will only receive a single exposure to study drug to minimize the potential for adverse effects from repeated drug exposure. The SRD TAK-071+donepezil cohorts (Cohorts 20 to 22) will establish a high well-tolerated dose of TAK-071 when coadministered with donepezil, and will help to determine the dose in the scopolamine PoM study.

Cohorts 18 and 19 (and additional cohorts, if needed) with dose(s) of 120 mg or higher dose are to explore the safety and tolerability of TAK-071 in single dose(s) of at least 120 mg, with a special focus on safety EEG. ^{CCI}

Optional cohorts have been included to allow the opportunity to explore higher exposures in the event that neither the NOAEL plasma exposure threshold nor the MTD are attained. Identifying a single TAK-071 dose that, while remaining appropriately below the 28-Day monkey NOAEL threshold, provides a high plasma exposure that is deemed to be of importance for the purposes of an upcoming PoM scopolamine challenge study (TAK-071-1002) in healthy subjects. This is because a high TAK-071 dose is expected to maximize the potential for observing a significant reversal of scopolamine-induced cognitive impairment.

The MRD (Cohorts 7 to 9) will allow for the characterization of the safety/tolerability and PK of repeated TAK-071 daily exposures over a limited duration of time, as well as the characterization of any time dependency in the PK in Cohort 9 (the highest dose). Subjects in the first MRD cohort (Cohorts 7) will only be dosed after confirmation of acceptable safety and tolerability and evaluation of the 24-hour plasma PK and 12-hour CSF PK data from Cohort 3. The

safety/tolerability and PK of repeated TAK-071 doses in combination with donepezil will be investigated in MRD Cohorts 10 to 12 in healthy subjects.

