Bowel function (r)	X	X	X	X	X	X	X	X	X	X	X	X	X	X	X	X	X	X	X	X	X	X	X	X	X	X	X	X	X	X	X	X	X	X	X	X	X	X	X	X	X	X	
C-SSRS (s)	X	X																																									
Pupil size (t)			X																																								

Footnotes are on the following page.

ET=Early Termination Visit, HBsAg=hepatitis B surface antigen, HCV=hepatitis C virus.

- (a) A PK blood sample should be collected at the Early Termination Visit if possible.
- (b) Follow-up will occur by telephone on Day 39 (± 2) unless abnormal clinically significant findings are observed upon discharge. In these cases, subjects must then be brought back to the clinic for re-evaluation per investigator's discretion.
- (c) Vital signs (oral temperature, respiration, pulse, and blood pressure) will be obtained as indicated.
- (d) Height and BMI will be collected at Screening only.
- (e) All ongoing medications will be recorded from Screening and throughout the study.
- (f) Blood and urine samples for clinical laboratory tests (hematology, coagulation, serum chemistry, urinalysis) will be collected as indicated. On Day 1, the urine sample for urinalysis will be taken at predose (within 2 hours prior to dosing) and the blood sample for these tests will be taken 1 hour postdose. On subsequent days, samples will be taken predose upon rising in the morning under fasted condition.
- (g) During the course of the study, regular serum hCG pregnancy tests will be performed for female subjects and subjects will receive continued guidance with respect to the avoidance of pregnancy as part of the study procedures. In addition to a negative serum hCG pregnancy test at Screening, female subjects must have a negative serum hCG pregnancy test at Check-in prior to receiving the first dose of study drug.
- (h) FSH concentration will be obtained from postmenopausal women (defined as continuous amenorrhea of at least 2 years and not surgically sterile).
- (i) A standard 12-lead ECG will be recorded at Screening, Check-in (Day -1), Days 1 and 8 (TAK-071 predose [within 60 minutes prior to dosing] and at 0.5, 1, 2, 4, and 8 hours postdose), and Days 2 to 7 and 9 to 30 upon morning rising, or ET. Single ECGs will be taken at all visits.
- (j) Continuous 12-lead Holter ECG monitoring will be conducted 2 hours predose until 48 hours postdose on Day 1 and 1 hour predose until 48 hours postdose on Day 28.
- (k) DIC will be dispensed for treatment.

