- (l) Blood samples for PGx analysis will be collected as follows: 6 mL for DNA on Day 1; 2 \times 2.5 mL for RNA predose TAK-071 on Day 1, predose TAK-071 on Day 8, and 12 hours postdose on Day 28.
- (m) Blood samples (3 mL/sample into EDTA coated tubes) for plasma measurement of TAK-071 will be collected predose (within 30 minutes prior to dosing) and specified time points outlined in Section [9.1.15.1](#).
- (n) Urine samples for PK analyses will be collected predose within approximately 1 hour of dosing and specified time points outlined in Section [9.1.15.2](#).
- (o) CSF (up to 1.25 mL/sample) will be obtained Day 28 at predose (within 30 minutes before dosing) and at 4, 8, 12, 24, and 36 hours post last dose. If not performed within the last 12 months prior to Screening, a lumbar x-ray will be performed at Screening in to ensure that there are no deformities that could interfere with insertion of an indwelling cannula for the subsequent collection of CSF.
- (p) PTEs will be collected from signing of informed consent up until dosing on Day 1.
- (q) Any event after dosing on Day 1 will be captured as an AE.
- (r) Bowel function will be assessed using the BSF scale and daily stool count.
- (s) C-SSRS will be determined as indicated. If clinically significant at Final Visit, C-SSRS will also be determined as part of the Follow-up Visit.
- (t) Pupil size will be measured at the time points outlined in Section [9.1.17.2](#).

ET=Early Termination Visit, HBsAg=hepatitis B surface antigen, HCV=hepatitis C virus.

- (a) A PK blood sample should be collected at the ET Visit if possible.
- (b) Follow-up will occur by telephone on Day 32 (± 2) unless abnormal clinically significant findings are observed upon discharge. In these cases, subjects must then be brought back to the clinic for re-evaluation per investigator's discretion.
- (c) Vital signs (oral temperature, respiration, pulse, and blood pressure) will be obtained as indicated. In addition, orthostatic blood pressure will be measured at predose and at 2, 4, 6, 8, and 12 hours postdose in the first 24 hours after the initial dose of TAK-071 and then daily afterwards while subjects are confined in the phase 1 unit as detailed in Section 9.1.6.
- (d) Height and BMI will be collected at Screening only.
- (e) All ongoing medications will be recorded from Screening and throughout the study.

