All individual vital signs that meet Takeda's predefined criteria for markedly abnormal values ([Appendix B](#)) will be listed. The number and percentage of subjects with at least one postdose markedly abnormal vital sign measurement will be summarized. The mapping of the subjects who meet the MAV criteria for postdose vital sign parameters will be listed as a table. All postdose vital signs, including both scheduled and unscheduled measurements, will be included in the MAV summaries.

7.12.4 12-Lead ECGs

For SRD Cohorts 1 to 6 and 18 to 22, a standard 12-lead ECG will be recorded at Screening, Check-in (Day -1), Day 1 (predose [within 60 minutes prior to dosing], and at 0.5, 1, 2, 4, and 8 hours postdose), Days 2 through 5 (upon morning rising)/ ET and at the Follow-up Visit. Single ECGs will be taken at all visits. Continuous 12-lead Holter ECG monitoring will be conducted from 2 hours predose until 48 hours postdose in Cohorts 2, 4, 6, 18, and 19 only.

For MRD healthy volunteer Cohorts 7 and 8, a standard 12-lead ECG will be recorded at Screening, Check-in (Day -1), Day 1 (TAK-071 predose [within 60 minutes prior to dosing] and

at 0.5, 1, 2, 4, and 8 hours postdose), Days 2 through 21 (predose), Days 22 and 23 (upon morning rising)/ ET and at the Follow-up Visit. Single ECGs will be taken at all visits. Continuous 12-lead Holter ECG monitoring will be conducted from 2 hours predose until 24 hours postdose TAK-071 on Day 1 and from 1 hour predose until 48 hours postdose TAK-071 on Day 21.

For MRD healthy volunteer Cohort 9, a standard 12-lead ECG will be recorded at Screening, Check-in (Day -1), Days 1 and 8 (TAK-071 predose [within 60 minutes prior to dosing] and at 0.5, 1, 2, 4, and 8 hours postdose), and Days 2 to 7 and 9 to 30 upon morning rising/ ET, and at the Follow-up Visit. Single ECGs will be taken at all visits. Continuous 12-lead Holter ECG monitoring will be conducted 2 hours predose until 48 hours postdose on Day 1 and 1 hour predose until 48 hours postdose on Day 28.

For MRD + Donepezil pretreatment healthy volunteer Cohorts 10 to 12, a standard 12-lead ECG will be recorded at Screening, Check-in (Day -22) (donepezil predose [within 60 minutes prior to dosing]), Day -1, Day 1 (TAK-071 predose [within 60 minutes prior to dosing] and at 0.5, 1, 2, 4, and 8 hours postdose), Days 2 to 21 (predose), and Days 22 to 23 (upon morning rising)/ ET and at the Follow-up Visit. Single ECGs will be taken at all visits.

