Appendix B Criteria for Markedly Abnormal Values for Vital Signs

Parameter	Unit	Lower Criteria	Upper Criteria
Pulse	bpm	<50	>120
Systolic blood pressure	mm Hg	<85	>180
Diastolic blood pressure	mm Hg	<50	>110
Body temperature	°C	<35.6	>37.7
Orthostatic systolic blood pressure	mm Hg	CHG <= -20	
Orthostatic diastolic blood pressure	mm Hg	CHG <= -10	
Orthostatic pulse	bpm		CHG >10

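### Cohort 9, the top planned multiple dose given alone to non-Japanese subjects, is never measured orthostatically, and the SAP has no number-assessed denominator, so its primary vital-sign MAV percentage is biased downward

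*Protocol*

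**What the plan says.** Protocol Section 9.1.6 sets two vital-sign schedules.

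- Most cohorts: "For Cohorts 2, 4 to 8, and 10 to 22, orthostatic blood pressure and pulse will be measured at predose", then at 2, 4, 6, 8 and 12 hours on Day 1, and afterwards on days in the unit.
- CSF cohorts: "in subjects who are undergoing CSF collection (Cohorts 3 and 9), vital signs include body temperature (oral), respiratory rate, supine blood pressure" and pulse. The only extra timed reading is this: "In addition, vital signs should be collected in Cohorts 3 and 9 at approximately 5 hour postdose on Day 1 and Day 8" (Day 8 in Cohort 9 only).

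The Cohort 9 schedule in Appendix A, footnote (c), reads only: "Vital signs (oral temperature, respiration, pulse, and blood pressure) will be obtained as indicated". The orthostatic sentence found in the other multiple-dose schedules is absent. SAP 7.12.3 omits it for Cohort 9 as well.

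Footnote (o) of the same schedule dates the procedure: "CSF (up to 1.25 mL/sample) will be obtained Day 28 at predose", with the last sample 36 hours after the last dose. Section 6.2.1 identifies Cohort 9 as the highest dose of Cohorts 7 to 9.

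On the analysis side, the percentage of subjects with at least one postdose vital-sign MAV is a primary safety endpoint (Protocol 5.2.1.1, SAP 5.1). SAP Appendix B lists "Orthostatic systolic blood pressure", orthostatic diastolic blood pressure and orthostatic pulse among its criteria. SAP 7.12.3 states: "The number and percentage of subjects with at least one postdose markedly abnormal vital sign measurement will be summarized". SAP 7.12 presents safety tables by pooled placebo and each dose level in the Safety Set.

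**The concern.** A subject who is never stood up cannot be flagged on a criterion that needs a standing reading. If such a subject stays in the denominator, not assessed is printed as not abnormal. Here that happens in the cohort where a dose-related effect would be looked for first, and in part of the placebo group it is compared with. The table would then show an apparent safety advantage at the top dose that comes from the measurement schedule. SAP 7.13.1 uses the unblinded interim results of these cohorts to support phase 2 protocol development, so the table has a reader who may act on it.

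**Working it through.** The documents give no expected MAV rate, so there is no stated figure to reproduce. The check has four steps.

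**1. Opportunities to be flagged.** Postdose orthostatic sets per subject:
- Cohorts 7, 8 and 10 to 12: 5 on Day 1 (2, 4, 6, 8, 12 h) + 22 daily (Days 2 to 23) = about 27.
- Cohorts 13 to 15: 5 + 29 (Days 2 to 30) = about 34.
- Cohort 9: 0.

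**2. Whether the CSF procedure explains the omission.** Protocol 7.4.1 requires recumbency because of CSF sampling. In Cohort 9 that covers Day 28 predose to 36 h. Days 1 to 27 have no CSF procedure, and subjects are confined throughout (6.1.2.1). Holter recording is not the reason either: Cohorts 7 and 8 wear a Holter on their first and last dosing days (Table 9.b) and still have orthostatic sets. Cohort 3 differs, because its CSF sampling falls on its single dosing day.

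**3. Criteria out of reach.** Appendix B has seven vital-sign parameters: pulse, systolic, diastolic, temperature, and the three orthostatic ones. Cohort 9 can meet four of the seven.

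**4. Direction and possible size.** Let pv be the chance that a subject has a non-orthostatic vital-sign MAV and po the chance of an orthostatic one. Both are assumptions, taken as independent and with no drug effect.
- Fully measured subject: 1 − (1 − pv)(1 − po).
- Cohort 9 subject: pv.
- Shortfall: (1 − pv) × po, which is positive whenever an orthostatic-only flag can occur.

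Illustration with pv = 10% and po = 20%: fully measured 1 − 0.90 × 0.80 = 28%; Cohort 9 10%; shortfall 18 points. Over pv 5% to 20% and po 5% to 70%, the shortfall runs from 0.80 × 0.05 = 4 points to 0.95 × 0.70 = about 67 points.

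The printed contrast with placebo depends on a layout that the SAP does not settle. Same illustration:

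| Layout | Top-dose column | Pooled placebo | Spurious difference |
|---|---|---|---|
| Donepezil cohorts separate (6 placebo, 2 unmeasured) | 10% | (4 × 28 + 2 × 10)/6 = 22% | −12 points |
| Placebo pooled over Cohorts 7 to 12 (12 placebo, 2 unmeasured), Cohort 9 in its own column | 10% | (10 × 28 + 2 × 10)/12 = 25% | −15 points |
| As above, Cohorts 9 and 12 sharing one dose column | (6 × 10 + 6 × 28)/12 = 19% | 25% | −6 points |

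The sign is the same in every row.

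**The case against.** Several points on the other side stand.

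- **Size.** A reader might infer that Cohort 9 would show 0% where Cohorts 7 and 8 show 24%, 42% or 75% (1 − 0.99^27, 1 − 0.98^27, 1 − 0.95^27). The documents do not support that. Those figures cover only the orthostatic component, use per-set rates with no source, and treat 27 readings in one person as independent. The four non-orthostatic criteria still apply to Cohort 9.
- **Same-dose data.** A reader might also infer that no orthostatic data exist at the top dose. Under Section 6.2.2.2, Cohort 15 (Japanese) is planned at the Cohort 9 dose and Cohort 12 (with donepezil) is intended to be. Both are measured orthostatically. What is missing is the top dose alone in non-Japanese subjects.
- **Denominator.** The SAP does not say outright that unmeasured subjects count as normal, nor that all criteria form one composite row. It says that missing data are not imputed (7.1.1). But it names the Safety Set and no number assessed. Splitting the table by parameter would not cure this by itself, because it would still allow 0 of 6 for something never measured.
- **Stakes.** Vital signs are not tested statistically, sample size is not power-based, and escalation rests on blinded review of each cohort (6.1.5), not on this table. Dizziness or lightheadedness can still be reported as an adverse event.
- **Timing.** Cohort 9 has probably been completed. Section 6.2.2.2 already reports tolerability in Cohort 12, and Section 13.2.1 has Cohort 16 enrolling while the other cohorts go to interim analysis. Neither document says so expressly.

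**Conclusion.** The concern holds as a measurement gap combined with an unspecified denominator. As the plan is written, the vital-sign MAV percentages for Cohort 9 and for the pooled placebo group are biased downward relative to cohorts with about 27 orthostatic sets per subject. The same mechanism affects Cohort 3 in the single-dose part. The direction follows from the schedule alone and fails only if no subject would have an orthostatic-only flag. The size cannot be derived from the documents: the 4 to 67 point range rests wholly on assumed per-subject rates and independence, and sharing a column with Cohort 12 would dilute the bias without removing it. The documents do not support a claim that the top dose has no orthostatic evidence, or that dose escalation was compromised.

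Cohort 1 is unresolved. Protocol 9.1.6 gives it supine readings only, and SAP 7.12.3 repeats this. But the Appendix A footnote, and the single-dose paragraph of that same SAP section, exempt only Cohort 3 from orthostatic readings.

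**What to change.** 1. **SAP 7.12.3.** Report the three orthostatic criteria on their own lines, with the denominator limited to subjects who have at least one postdose orthostatic set. Apply the same limit to placebo subjects.
2. **SAP 7.12.3.** Base any any-vital-sign MAV percentage compared across doses on the four non-orthostatic criteria, which all cohorts can meet. State whether Cohorts 9 and 12 share a dose column.
3. **Cohort 1.** Reconcile Protocol 9.1.6 with the Appendix A footnote and the two statements in SAP 7.12.3. A denominator of subjects actually measured works either way.
4. **Only if Cohort 9 has not been dosed.** Amend Protocol 9.1.6 and the Cohort 9 footnote (c) to collect orthostatic blood pressure and pulse on the Cohort 7 and 8 schedule through Day 27, with supine readings from Day 28 for the CSF procedure. If Cohort 9 is complete, items 1 and 2 correct the table without new data.

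The cost is SAP wording and smaller stated denominators. Item 4 would add a few minutes per check in subjects who are already confined.
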